1 PROTOCOL SUMMARY

[figure not shown]
1.1 SYNOPSIS

Title:	HEART Camp Connect: A Feasibility Study
Grant Number:	NA
Study Description:	The proposed study uses a technology-facilitated, theory-based intervention to help patients with HFpEF start and continue an exercise program over time. This feasibility, pilot study will give us data to refine the intervention and allow us to gather preliminary data for a competitive application to a federal funder.
Objectives:	Our overall objectives for this study are to: (1) evaluate the feasibility of a virtual, theory based exercise training and coaching intervention in adults with HFpEF; and (2) examine the preliminary effects of this intervention on adherence to exercise, physical function, key inflammatory markers, and patient-reported outcomes.
Endpoints:	Primary Endpoint: 3 months Secondary Endpoints: 6 months
Study Population:	We will enroll 25 participants with heart failure with preserved ejection fraction 19 years of age or older from Nebraska Medicine in Omaha, Nebraska.
Phase:	Feasibility
Description of Sites/Facilities Enrolling Participants:	Single site study, recruiting in the U.S. only at Nebraska Medicine in Omaha, Nebraska
Description of Study Intervention/Experimental Manipulation:	Participants are randomized to enhanced usual care or a 3 month coaching intervention.
Study Duration:	24 months
Participant Duration:	6 months

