1.3 SCHEDULE OF ACTIVITIES

	Pre-screening (Pre-consent)	Visit 1 Week 0	Visit 2 Week 12	Visit 3 – Final Week 24
EMR Review Eligibility	X			
Informed Consent		X		
Cardiopulmonary exercise test		X		
Demographics		X		
Clinical history		X	X	X
Height & Weight		X	X	X
Randomization		X		
Coaching Intervention*		*	*	*
Adverse Events Reporting		X	X	X
Feasibility Outcome Evaluations				
Recruitment and retention	X	X	X	X
Coach availability	X	X	X	X
Smart device availability	X	X	X	X
Connectivity issues	X	X	X	X
Patient Outcome Evaluation				
Intervention Acceptability				X
Pain Assessment (Brief Pain Inventory)		X	X	X
Quality of Life Questionnaire		X	X	X
Cognition		X	X	X
Health Status		X	X	X
Minutes of Exercise		X	X	X

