2 INTRODUCTION

2.1 STUDY RATIONALE

Despite the worldwide acknowledgment of exercise as a beneficial, non-pharmacological therapy for patients with heart failure (HF), many patients, particularly those with heart failure with preserved ejection fraction (HFpEF), do not engage in regular exercise and are unable to sustain exercise once started in a program. Patients with HFpEF report difficulties finding a routine place to exercise that includes support and accountability delivered near their home as barriers to continued exercise. These challenges are exacerbated by the ongoing COVID-19 pandemic. Therefore, we propose HEART Camp Connect that builds on the previously efficacious HEART Camp intervention. The primary objective of this study is to establish the feasibility and preliminary efficacy of the HEART Camp Connect intervention in patients with heart failure with preserved ejection fraction. We will accomplish this objective with two aims. Aim 1 examines the feasibility of administering HEART Camp Connect to patients with HFpEF. Our feasibility assessment will focus on process (e.g. recruitment rates, retention), resources (e.g. physical capacity, staff availability), management (e.g. data capture and management), and science (e.g. testing psychometrics of tools in the HFpEF population). Aim 2 tests the preliminary effects of HEART Camp Connect compared to enhanced usual care on adherence to exercise, physical activity, function, inflammation, patient-reported outcomes, and our theory-based interventional components. Impact: Exercise benefits patients with HFpEF by reducing morbidity and mortality and improving symptoms and quality of life. The proposed study uses a technology facilitated, theory-based intervention to help patients with HFpEF start and continue an exercise program over time. This feasibility, pilot study will give us data to refine the intervention and allow us to gather preliminary data for a competitive application to a federal funder.

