HFpEF with ejection fractions ranging from 40 to 50% and above. The validated H2FPEF algorithm¹⁷ is now available to identify HFpEF which we incorporate into our inclusion/exclusion criteria. 3. Prior exercise interventions tested in HF were not specifically designed to promote adherence using theory-based components. HEART Camp Connect is designed to promote adherence to exercise by supporting the adoption and maintenance of exercise behavior. 4. Adherence is inconsistently defined across studies and often not objectively measured. Several studies use session attendance as a measure of adherence, but this does not allow for examination of dose-response effects or comparison to other clinically meaningful outcomes.¹⁸⁻²⁰

In this study, we monitor coaching session attendance and measure adherence objectively using minutes of moderate intensity exercise from a heart rate monitor. 5. No studies have tested interventional effects on inflammatory biomarkers, despite the known relationship between HFpEF and inflammation.²¹ This pilot incorporates examination of the impact of exercise on inflammatory biomarkers. 6. Cardiac rehabilitation is the predominate model for exercise in adults with HF, but the program is not specifically designed for adults with HFpEF and current Medicare guidelines do not reimburse attendance.²² Further, exercise is rarely sustained after program completion and programs are often inaccessible. This has resulted in notoriously low attendance at cardiac rehabilitation and subsequent poor long-term adherence to exercise.²³⁻²⁷ Our intervention is delivered virtually making exercise content accessible to participants at any time to improve sustainability.

Adherence is the Achilles heel of exercise in HF. The 2013 ACCF/AHA Guideline for the Management of Heart Failure recommends exercise as a non-pharmacological therapy that is safe and effective for individuals with HF (Class I - Level of Evidence A).¹⁰ Yet, studies indicate that as many as 91% of patients with HF do not participate in regular exercise.²⁸⁻³⁰ Therefore, promoting adherence to exercise in HF, particularly HFpEF, is a major priority for the National Heart Lung and Blood Institute (NHLBI) and the long-term goal of this proposal.³¹

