HFpEF and exercise in HFpEF are assigned a high priority status by the NHLBI. The NHLBI convened two working groups, one addressed exercise as a non-pharmacological treatment for HF (2015)⁷ and the other (2019)³¹ identified knowledge gaps and set priorities for HFpEF research in the next 10 years. The HFpEF working group urged the development of effective HFpEF treatment strategies and referred to HFpEF as the greatest unmet need in cardiovascular medicine today. The panels set several priority targets for future study, including: 1. to examine optimal strategies and interventions to promote exercise initiation and adherence; 2. to identify behavioral mechanisms to improve adherence to exercise in HF; and 3. examine longitudinal changes in inflammatory biomarkers to better understand correlates to clinical status in HFpEF.^{7,31} This proposal addresses these high priority areas by evaluating the feasibility, acceptability and preliminary efficacy of HEART Camp Connect in promoting adherence to exercise, and physical activity and function, inflammatory markers, patient-reported outcomes, and theory-based components in HFpEF.

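### Sample size is stated two ways, three Aim 2 outcomes do not line up with the schedule or endpoints, and no section commits to reporting spread

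*Combined protocol and SAP*

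**What the plan says.** **Sample size.** The synopsis (1.1) states: "We will enroll 25 participants with heart failure with preserved ejection fraction". Section 6.1.1 attaches n=25 to HEART Camp Connect in the sentence that introduces weekly coaching. Section 6.3 randomizes 1:1. Section 9.2 says the number reflects expected recruitment and gives no figure.

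**Outcomes.** The synopsis sets out to "examine the preliminary effects of this intervention on adherence to exercise, physical function, key inflammatory markers, and patient-reported outcomes". Section 2.1 says "Aim 2 tests the preliminary effects of HEART Camp Connect compared to enhanced usual care" and adds physical activity and theory-based components to the list. Section 2.2 commits to biomarkers, "This pilot incorporates examination of the impact of exercise on inflammatory biomarkers", and closes by naming "inflammatory markers, patient-reported outcomes, and theory-based components in HFpEF" among the things evaluated. Section 2.3 treats venipuncture as a study risk and says where blood will be taken.

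**Schedule and endpoints.** The schedule (1.3) has no blood or biomarker row and no row for theory-based measures. Cardiopulmonary exercise testing (CPET) appears at Week 0 only, and section 8.2 calls it a baseline safety evaluation. Section 3 lists minutes of exercise as secondary, and symptoms, quality of life and interventional mechanisms as tertiary. Section 9.1 lists exercise, symptoms and quality of life. Section 9.4.9 (exploratory analyses) is marked not applicable.

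**Analysis.** Section 9.4.1 confines the report to counts, proportions and means. Section 9.4.3 leaves the secondary endpoints to whatever descriptive statistics are appropriate. Section 9.3 rules out inference. The synopsis and section 4.2 give the purpose: preliminary data and tested strategies for a larger trial.

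**The concern.** A pilot of this kind has two products: an account of feasibility, and preliminary data for the next application. Both need a definite number of participants. Recruitment is itself a feasibility outcome in 1.3, and a recruitment result cannot be judged against a target that could be 25 or 50.

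The preliminary data also need each stated outcome to have a time point and a place in the endpoint list. As the text stands, a reader cannot tell when inflammation would be measured or under which endpoint it would be reported, although venipuncture is presented as a risk to participants. Theory-based components and function each have part of this chain missing.

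For the outcomes that are scheduled, arm means without a measure of spread do not show how variable participants are. That is the quantity a larger trial needs from a small one.

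**Working it through.** **1. Sample size.** Inputs: 25 enrolled (1.1), n=25 in the coaching arm (6.1.1), 1:1 allocation (6.3). The plan disclaims a power calculation, so there is no formula to reproduce.

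- Reading A, 25 in total: 25 / 2 = 12.5, so 12 and 13 per arm.
- Reading B, 25 in the coaching arm: 25 × 2 = 50 in total, 25 per arm.

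Sections 1.1 and 6.1.1 cannot both hold under 6.3.

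**2. What the conflict does to precision.** The half-width of a 95% interval for a difference in means, in SD units, is t(0.975, df) × √(1/n₁ + 1/n₂). The 95% limits for a pooled SD are the estimate times √(df/χ²), using the upper and lower 2.5% points of chi-square.

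| | 12/13 (df 23) | 25/25 (df 48) |
|---|---|---|
| Half-width | 2.069 × 0.400 = 0.83 SD | 2.011 × 0.283 = 0.57 SD |
| Pooled SD factors | 0.78 to 1.40 | 0.83 to 1.25 |
| Squared: effect on a later trial's n | 0.60 to 1.97 | 0.70 to 1.56 |

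With an assumed 20% dropout (the plan gives no figure), the arms become 10/10 and 20/20 and the half-widths 0.94 and 0.64 SD. All of these assume roughly normal data, which exercise minutes may not be. They show how much depends on which N is meant. They do not measure the mismatch of outcomes.

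**3. Outcomes, side by side.**

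| Outcome | Objective | Row in 1.3 after baseline | Endpoint |
|---|---|---|---|
| Inflammatory markers | 1.1, 2.1, 2.2 | None | None in section 3 or 9.1 |
| Theory-based components | 2.1, 2.2 | None | Tertiary in section 3; not in 9.1; 9.4.9 not applicable |
| Physical function | 1.1, 2.1, 2.2 | None identified; CPET is Week 0 only | None in section 3 or 9.1 |

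For contrast, adherence has a row for minutes of exercise at Weeks 0, 12 and 24, and patient-reported rows for pain, quality of life, cognition and health status run at the same visits.

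**4. Why spread matters.** For a fixed difference of 1 unit, assuming two-sided alpha 0.05 and 80% power, n per arm is 2 × (1.960 + 0.842)² × SD², rounded up:

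- SD 1.0: 15.7, so 16
- SD 1.5: 35.3, so 36
- SD 2.0: 62.8, so 63

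The same difference in means can therefore call for 16 or 63 per arm. Means alone do not settle the size of a later trial.

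**The case against.** **It is an openly descriptive pilot.** Section 3 says the study is not powered to test an effect, and section 9.3 excludes inference. Both statements stand. The absence of a power calculation is disclosed and is not a fault, and a between-arm interval is a preference rather than a correction.

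**An SD is not forbidden.** Section 9.4.3 covers the secondary endpoints and leaves room for one. Section 10.1.4 keeps de-identified data for later use, so an SD could be computed afterwards. A reader might infer that the trial will leave no estimate of variability. The documents do not support that. What stands is that no section commits to reporting spread, and that 9.4.1 read literally leaves it out.

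**Measures may be collected but recorded elsewhere.** A reader might infer that biomarkers, function or theory-based measures will not be collected at all. That also goes too far. Section 2.3 describes blood draws and says they will be combined with clinical draws where possible, which might explain the lack of a fixed visit. The Health Status or quality-of-life instrument may contain a function domain. The flow diagram in 1.2 and the schedule's footnote are not shown, and the manual of procedures is not available. The mismatch among the sections shown remains.

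**The n=25 in 6.1.1 may be the study total, loosely placed,** since HEART Camp Connect is also the study's name. That is possible, but the sentence describes coaching, which only one arm receives. The text shown does not settle it.

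**Conclusion.** The point holds in three limited parts.

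- **Sample size.** The two statements conflict by a factor of two under 1:1 allocation. The missing flow diagram might resolve it; section 9.2 does not. Neither reading can be called the right one from the text.
- **Outcomes.** Inflammation has neither a schedule row nor an endpoint. Theory-based components have an endpoint without a row. Function has no identified measure after baseline. This is a mismatch between sections in the text shown, not evidence that data will go uncollected.
- **Spread.** Nothing commits to an SD, although the pilot's purpose calls for one. This is a gap in commitment, not a prohibition.

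The primary feasibility objective survives, apart from its unclear recruitment target. The precision figures rest on approximate normality and, where stated, an assumed 20% dropout. The inconsistencies themselves rest on no numerical assumption.

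**What to change.** 1. State whether 25 is the total or the size of the coaching arm, and make 1.1 and 6.1.1 agree. This costs one sentence.
2. In 9.4.1 and 9.4.3, replace the restriction to means with means and SDs by arm at Weeks 0, 12 and 24, or medians and interquartile ranges where the data are skewed. This is a few lines of analysis on data already scheduled. A descriptive between-arm difference with a 95% interval and no p-value is optional.
3. Reconcile the objectives in 1.1, 2.1 and 2.2 with 1.3, section 3 and 9.1. Where inflammatory markers, theory-based measures or function are already collected, give each a visit and an endpoint. Where they are not, remove them from the objectives. No new procedures are needed, so the cost is protocol text.

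The downside is a possibly narrower Aim 2 and summaries whose spread is visibly wide.

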1.2 SCHEMA

This section should include a diagram or flowchart that provides a quick “snapshot” of the study and ideally is limited to 1 page. Below is an example schematic that shows the level of detail needed to convey an overview of the study design. Revise with study-specific information and adapt the diagram to illustrate your study design (e.g., changing method of assignment to study group, adding study arms, visits, etc.). The time point(s) indicated in the schematic should correspond to the time point(s) in Section 1.3, Schedule of Activities, e.g., Visit 1, Day 1; Visit 2, Day 14 ± 7; etc. Although the convention is to call contacts with participants “Visit 1, Visit 2, etc.,” participant contacts in which data will be collected remotely without an in-person visit should also be included in this schematic. One alternative is to use the term “Time 1, Time 2, etc.” to accommodate both in-person visits and assessments conducted remotely.

Study Flow Diagram

1.3 SCHEDULE OF ACTIVITIES

	Pre-screening (Pre-consent)	Visit 1 Week 0	Visit 2 Week 12	Visit 3 – Final Week 24
EMR Review Eligibility	X			
Informed Consent		X		
Cardiopulmonary exercise test		X		
Demographics		X		
Clinical history		X	X	X
Height & Weight		X	X	X
Randomization		X		
Coaching Intervention*		*	*	*
Adverse Events Reporting		X	X	X
Feasibility Outcome Evaluations				
Recruitment and retention	X	X	X	X
Coach availability	X	X	X	X
Smart device availability	X	X	X	X
Connectivity issues	X	X	X	X
Patient Outcome Evaluation				
Intervention Acceptability				X
Pain Assessment (Brief Pain Inventory)		X	X	X
Quality of Life Questionnaire		X	X	X
Cognition		X	X	X
Health Status		X	X	X
Minutes of Exercise		X	X	X

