3 OBJECTIVES AND ENDPOINTS

OBJECTIVES	ENDPOINTS	JUSTIFICATION FOR ENDPOINTS
Primary		
Assessment of Feasibility & Acceptability	Process, resources, procedures, data management, fidelity, acceptability	Needed to refine intervention for future testing
Secondary		
Preliminary effects on exercise	Minutes of exercise/week	We are not statistically powered to test for an effect
Tertiary/Exploratory		
Preliminary effects on symptoms & interventional strategies	Symptoms, quality of life, interventional mechanisms	Evaluate symptoms and intervention strategies

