6.1.1 STUDY INTERVENTION

The HEART Camp Connect intervention is founded in social-cognitive theory⁴⁶ and the future-oriented motivation and self-regulation model proposed by Miller and Brickman.⁴⁷ HEART Camp Connect (n=25) includes weekly virtual coaching sessions with experienced coaches from Engage. For 3 weeks per month, coaches and participants meet 1-on-1 via videoconference to review heart rate data, exercise diaries from the prior week and initiate discussion related to behavioral change mechanisms. One week per month HEART Camp Connect participants will be assigned to a small group (1 coach:5 participants) exercise/observation session. During these sessions, coaches will demonstrate exercises and observe participants via videoconference for proper form and real-time encouragement in a group setting. Coaches will call any HEART Camp Connect participant that fails to

attend their scheduled weekly coaching session for 2 consecutive weeks. Participants achieving a minimum of 120 minutes of moderate-intensity exercise per week on average weeks 1-12 will be given the option to opt-out of coaching sessions for weeks 13-16. We recognize that this could potentially create variation in the dose of the coaching and therefore, will closely monitor the minutes of coaching per participant throughout the study. We will also closely monitor adherence during this time. Participants that relapse (become non-adherent for 2 consecutive weeks) for any reason (e.g., hospitalization, loss of motivation) will return to weekly coaching for the remainder of the intervention. Testing optional coaching is part of our feasibility assessment and increases the future scalability of this intervention. In the sustainability period (Weeks 17-24), weekly coaching stops, and HEART Camp Connect participants are expected to self-regulate exercise and maintain adherence.

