7.1 DISCONTINUATION OF STUDY INTERVENTION/EXPERIMENTAL MANIPULATION

If patients are unable to safely complete the CPET or if their CPET results indicate they exceed our thresholds for cardiorespiratory fitness, they will be immediately withdrawn from the study. If the patient withdraws consent, the patient will be removed from the research study..

When a subject discontinues from HEART Camp Connect but not from the study, remaining study procedures will be completed as indicated by the study protocol. If a clinically significant finding is identified (including, but not limited to changes from baseline) after enrollment, the investigator or qualified designee will determine if any change in participant management is needed. Any new clinically relevant finding will be reported as an adverse event (AE).

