7.2 PARTICIPANT DISCONTINUATION/WITHDRAWAL FROM THE STUDY

Participants are free to withdraw from participation in the study at any time upon request.

An investigator may discontinue a participant from the study for the following reasons:

- Significant study intervention non-compliance, unless varying compliance is an aspect of the study objectives
- Lost-to-follow up; unable to contact subject (see **Section 7.3, Lost to Follow-Up**)
- Any event or medical condition or situation occurs such that continued collection of follow-up study data would not be in the best interest of the participant or might require an additional treatment that would confound the interpretation of the study
- The participant meets an exclusion criterion (either newly developed or not previously recognized) that precludes further study participation
-

The reason for participant discontinuation or withdrawal from the study will be recorded. Subjects who sign the informed consent form and are randomized but do not receive the study intervention may be replaced. Subjects who sign the informed consent form, and are randomized and receive the study intervention, and subsequently withdraw, or are discontinued from the study, will not be replaced.

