9 STATISTICAL CONSIDERATIONS

9.1 STATISTICAL HYPOTHESES

We do not have a separate statistical plan for this pilot study.

- Primary Endpoint(s): Feasibility and acceptability
- Secondary Endpoint(s): Exercise, symptoms, quality of life

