9.4.2 ANALYSIS OF THE PRIMARY ENDPOINT(S)

- *We will describe feasibility and acceptability.*

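### Acceptability, part of the primary endpoint, is collected only at Week 24 with no exit assessment, so it will probably be overstated if people who leave the study are less satisfied

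*Combined protocol and SAP*

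**What the plan says.** Acceptability is primary in two places. The objectives table in section 3 lists the primary endpoints as "Process, resources, procedures, data management, fidelity, acceptability", and section 9.1 has "Primary Endpoint(s): Feasibility and acceptability". Section 3 gives the purpose as refining the intervention before further testing.

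In section 1.3 the row "Intervention Acceptability" has one mark, under Visit 3, Week 24. It has none at Week 12, and the schedule has no early-termination column. The pain, quality-of-life, cognition and health-status measures are marked at Weeks 0, 12 and 24.

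Two groups are treated differently:
- Those who stop coaching only. Section 7.1: "When a subject discontinues from HEART Camp Connect but not from the study, remaining study procedures will be completed". They are still due the Week 24 items.
- Those who leave the study. Section 7.2: "The reason for participant discontinuation or withdrawal from the study will be recorded". No exit questionnaire is specified. Under section 7.3, a person who cannot be reached has loss to follow-up entered as the primary reason.

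The whole primary analysis in section 9.4.2 is "We will describe feasibility and acceptability". Section 9.3 defines no analysis population. No section gives an acceptability instrument, denominator, missing-data rule or target.

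**The concern.** The acceptability figure will rest on people still in the study at 24 weeks. Whether someone stays may depend on how acceptable the coaching was, so the respondents may be selected by the thing being measured. Section 6.1.1 says "In the sustainability period (Weeks 17-24), weekly coaching stops", so a person who leaves during coaching, or in the eight weeks after it, goes unrated. Because acceptability has no earlier assessment, there is no previous value to fall back on. Section 7.2 adds another route: subject to an exception, the investigator may discontinue a participant for marked non-compliance, and people who dislike the coaching are plausible non-compliers.

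The pilot exists to refine the intervention. Those who left because of the coaching could say most about what to change, and as written the plan never puts the acceptability items to them. A favourable completers-only figure could then be carried into the larger application.

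**Working it through.** The plan states no acceptability figure, target or dropout rate, so there is nothing to reproduce. What can be checked is how far a completers-only figure could differ from the figure for everyone randomised to coaching.

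**Inputs from the documents.** Total enrolment is 25 (section 1.1) and allocation is 1:1 (section 6.3), so 25/2 = 12.5, about 12 or 13 coached. Section 6.1.1 instead gives n=25 for the coached arm. The two cannot both hold, so both sizes are shown.

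**Assumed inputs.** Share of coached participants without a Week 24 rating, d: 10% to 30%. Acceptability among completers, p_c: 80% to 90%. Acceptability among leavers, p_l: from 0% up to p_c. Treating acceptability as yes/no is also an assumption. Section 9.4.1 allows means as well as proportions, and the formula below works for mean scores in the same way.

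**Overstatement.** The figure for everyone is (1 − d) × p_c + d × p_l. Subtracting it from p_c gives

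overstatement = d × (p_c − p_l).

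- Leavers rate coaching as completers do (p_l = p_c): 0 points for any d.
- Half of leavers find it acceptable (p_l = 50%), d = 20%, p_c = 90%: 0.20 × 0.40 = 8 points.
- No leaver finds it acceptable (p_l = 0): 8 to 9 points at d = 10%, 16 to 18 at d = 20%, 24 to 27 at d = 30%.

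**Bounds in whole participants.** Each row assumes exactly one dissatisfied completer. The worst case counts every leaver as dissatisfied, the best case as satisfied.

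| Coached | Lost | Completers only | Worst case | Best case | Completers minus worst |
|---|---|---|---|---|---|
| 13 | 1 | 11/12 = 92% | 11/13 = 85% | 12/13 = 92% | 7 points |
| 13 | 2 | 10/11 = 91% | 10/13 = 77% | 12/13 = 92% | 14 points |
| 13 | 3 | 9/10 = 90% | 9/13 = 69% | 12/13 = 92% | 21 points |
| 13 | 4 | 8/9 = 89% | 8/13 = 62% | 12/13 = 92% | 27 points |

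If 25 are coached and 5 are lost, with two dissatisfied completers, 18/20 = 90% is compatible with 18/25 = 72% to 23/25 = 92%.

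Read the table across each row. Differences between rows also reflect a change in the assumed number of dissatisfied people (2, 3, 4 and 5 of 13 in the worst case), so they do not measure selection. Within rows, a completers-only figure near 90% says little about everyone assigned to coaching once two or three of 13 are missing.

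**The case against.** A reader might infer that anyone put off by the coaching never counts. The documents do not support that. Section 7.1 keeps people who stop coaching but stay in the study due for the Week 24 items. Study leavers have a reason recorded and count in retention, a feasibility outcome marked at every column of section 1.3. Coaching attendance and minutes are also monitored, and coaches call anyone who misses two consecutive weekly sessions (sections 2.2 and 6.1.1). This stands, and it limits the point to people who leave the study or otherwise have no Week 24 assessment. It does not close the gap: retention mixes illness, logistics and dissatisfaction, and a recorded reason is not an answer to the acceptability items.

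A reader might also take upward bias as certain. It is not. People may leave for medical reasons or be lost for reasons unrelated to coaching, and if leavers are as satisfied as completers the bias is zero.

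Nor is acceptability shown to be half of the primary endpoint: section 3 lists it as one of six components, without weights. The analysis is descriptive with no go/no-go rule, so no planned decision turns on this figure. That lowers the stakes, but the figure still informs the refinement the pilot is meant to support.

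Lastly, counting every non-responder as finding the coaching unacceptable would label medical withdrawals as critics. That is right, and it is why the worst case should appear only as one of two bounds.

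**Conclusion.** The point holds in limited form and the plan should be changed. Acceptability is part of the primary endpoint and is asked only at Week 24, so participants who leave the study earlier give no rating. If they are less satisfied than completers, the reported figure will be too high.

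The documents do not allow the size to be estimated. Over the assumed ranges (10% to 30% lost, 80% to 90% acceptability among completers) the overstatement runs from 0 to 27 points. The central illustration, 13 coached and 3 lost, leaves an observed 90% compatible with 69% to 92%. It rests on 25 enrolled at 1:1, a yes/no measure and an assumed loss; a coached arm of 25 would dilute each loss.

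The point concerns who is asked. The synopsis timing, "Primary Endpoint: 3 months Secondary Endpoints: 6 months", also does not fit an acceptability measure taken only at Week 24. That mismatch, and the two statements of the coached arm's size, need reconciling separately.

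**What to change.** In section 1.3, add the same acceptability items, given remotely, when a coached participant stops coaching or leaves the study, as well as at the scheduled visit. Offer them only to those who still agree to be contacted. Section 7.1 removes people who withdraw consent from the study, so the consent form should describe the exit items in advance.

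In section 9.4.2, specify:
- the responders-only figure, with the number responding out of all randomised to coaching;
- worst-case and best-case bounds for non-responders;
- withdrawal reasons tabulated beside these figures;
- how anyone randomised to coaching but replaced under section 7.2 is counted.

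The cost is one short REDCap form triggered at discontinuation, a sentence in the consent form and a few table lines. Some leavers will not respond, so the gap will narrow rather than close, and the bounds may look less favourable than a completers-only percentage.
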